4.0 PATIENT ELIGIBILITY CRITERIA

Inclusion criteria

1. Diagnosis of MF (either primary or post essential thrombocythemia/polycythemia vera) requiring therapy, including those previously treated and relapsed or refractory, or if newly diagnosed, with intermediate-1 or -2 or high risk according to International Prognostic Scoring System (IPSS).
2. Palpable splenomegaly of more than or equal to 5 cm below left costal margin on physical exam
3. Understanding and voluntary signing an IRB-approved informed consent form.
4. Age \geq 18 years at the time of signing the informed consent.
5. Disease-free of other malignancies.
6. ECOG performance status 0 to 2.

7. Negative pregnancy test in females of childbearing potential (FCBP)[†] Male patients with female partners of child-bearing potential and female patients of childbearing potential are required to use two forms of acceptable contraception, including one barrier method, during their participation in the study and for 30 days following last dose. Acceptable forms of contraception include 1 highly effective method such as an intrauterine device (IUD), hormonal (birth control pills, injections, or implants), tubal ligation, or partner's vasectomy and at least 1 additional approved barrier method such as a latex condom, diaphragm, or cervical cap. Female patients of childbearing potential must not be breast-feeding or planning to breast feed and must have a negative pregnancy test \leq 7 days before first study treatment.
8. QTcF interval \leq 470 msec
9. Normal serum potassium and magnesium levels
10. Adequate organ function as demonstrated by the following:
 - Direct bilirubin \leq 2.0 mg/dL
 - Serum creatinine \leq 2.0 mg/dL.
 - SGPT \leq 3 x upper limit of normal (unless considered to be related to MF or patient has known history of Gilberts)
11. Platelets $>/= 50 \times 10^9/L$
12. ANC $>/= 1 \times 10^9/L$

Exclusion Criteria

1. Prior therapy with a JAK inhibitor (other than ruxolitinib for less than 3 months duration and currently on it) or HDACi. Patients that are currently on ruxolitinib for less than 3 months of therapy are eligible.
2. Use of any other standard or experimental therapy within 14 days of starting study therapy.
3. Lack of recovery from all toxicity from previous therapy to grade 1 or baseline.
4. Suspected pregnancy, pregnant or lactating females.
5. Any condition, including the presence of laboratory abnormalities, which in the opinion of the treating physician places the subject at unacceptable risk if he/she were to participate in the study or confounds the ability to interpret data from the study.
6. Known positive for HIV or infectious hepatitis, type A, B or C.
7. Patients with gastrointestinal (GI) tract disease, causing the inability to take oral medication, malabsorption syndrome, a requirement for intravenous (IV) alimentation, prior surgical procedures affecting absorption, uncontrolled inflammatory GI disease (e.g., Crohn's disease, ulcerative colitis)
8. Cardiopulmonary function criteria:
 - Current unstable arrhythmia requiring treatment
 - History of symptomatic congestive heart failure (New York Heart Association [NYHA] Class III or IV)
 - History of myocardial infarction within 6 months of enrollment

[†] A female of childbearing potential is a sexually mature woman who: 1) has not undergone a hysterectomy or bilateral oophorectomy; or 2) has not been naturally postmenopausal for at least 24 consecutive months (i.e., has had menses at any time in the preceding 24 consecutive months).

- Current unstable angina
- Family history of long QT syndrome

5.0 TREATMENT PLAN

On this study 4 weeks of therapy is considered one cycle of therapy. Ruxolitinib and pracinostat will be given orally in an outpatient setting. Ruxolitinib will be given continuously daily in 28-day cycles. Patients will receive ruxolitinib alone for the first 3 months, and then pracinostat will be added. Ruxolitinib provides maximum benefit usually within 3 months, therefore we add another agent to ruxolitinib after those initial 3 months, in order not to compromise benefit of ruxolitinib with some new side effect from additional medication (pracinostat in this case). Starting dose of ruxolitinib will be based on patients' platelet count, as per standard practice: 15 mg twice a day (BID) for patients with baseline platelet counts of $100\text{--}200 \times 10^9/\text{L}$ and 20 mg BID for those with baseline platelet counts $>200 \times 10^9/\text{L}$. For patients with platelet counts of $50\text{--}99 \times 10^9/\text{L}$, gradual up-titration from a starting dose of 5 mg BID is recommended. Dose of ruxolitinib may be increased or decreased at the discretion of the treating physician prior to initiation of pracinostat (see section 5.1). Patients who started ruxolitinib before enrollment into this study, will have the time they have been on ruxolitinib therapy counted toward the 3 cycles of ruxolitinib monotherapy, as per protocol. When a dosage change of the Ruxolitinib is indicated (except for holding therapy due to toxicity) patients will continue taking their previously prescribed dosing level until the new supply of Ruxolitinib is available for use by the patient.

Pracinostat is supplied as 45 and 60 mg capsules and will be self-administered (by the patient) one-time each day, 3 days a week for 3 weeks with doses approximately 48 hours apart, followed by one week of rest. Study medication will be taken approximately 30 minutes before a meal (e.g. breakfast) or ≥ 2 hours after a meal at approximately the same time each of the 3 days weekly (e.g., Monday, Wednesday, and Friday). Treatment cycles will be repeated every 28 days, unless delayed due to toxicity. Pracinostat should be taken with a glass of water; pracinostat is not to be taken with grapefruit or any other juice. Patients should be instructed to swallow the capsules whole and to not chew or crush them. If vomiting occurs, no attempt should be made to replace the vomited dose. Nicotine may alter metabolism of pracinostat such that potential efficacy may be decreased and therefore we will encourage smoking cessation while on study.

If the patient forgets to take his/her dose before noon, then the dose should be withheld that day and restarted the next dosing day in order to ensure approximately 48 hours between each dose. For example, if a patient misses a dose on Monday, the dose can be restarted on Tuesday, and the other doses would be taken on Thursday and Saturday.

Dosage of either drug for cycles can be reduced, increased or delayed based on the assessment of efficacy (lack of it) or due to adverse events, if any occur. Guidelines for reducing or increasing dosages are described in Section 5.1. Delays of a maximum of 8 weeks are allowed from scheduled next cycle.

Subjects will be asked to maintain a diary to record drug administration. Subjects will be asked to bring any unused study drug to the research center at their next visit. Research personnel will count and record the number of used and unused study drug capsules/tablets at each visit and reconcile with the subject diary. The study coordinator will question the patient regarding adherence to the dosing regimen, record the number of capsules/tablets and strengths returned, the date returned and determine treatment compliance before dispensing new medication to the study patient. Compliance below 80% will require counseling of the patient by study site personnel. Attempt will be made to provide an adequate treatment period of at least 6 months unless significant toxicity observed, to account for delayed time to response observed with biologic agents. Patients experiencing clinical benefit will continue therapy for 4 years unless progression of disease or toxicity warranting discontinuation of therapy is observed.

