5.1 Dose Modification

Non-hematologic toxicity:

If drug-related grade 3 or 4 non-hematologic toxicity is attributable to one or both of the drugs, dose interruption of the drug(s) causing the toxicity, as assessed by the treating physician, is mandatory. Patient who experience grade 3 drug related non-hematological toxicity may be given a subsequent course one dose level below the previous course, but the patient must have recovered to grade </=1 or baseline before institution of the next course. If a patient has drug-related grade 4 non-hematologic toxicity, he/she may receive a subsequent courses at one reduced dose level after resolution of toxicity to grade </=1, only if approved by the Principal Investigator based on the clinical significance of the toxicity and only if patient has had derived a benefit from the therapy. The dose of therapeutic agents can be decreased at the discretion of treating physician, for chronic grade 2 non-hematologic toxicity. In specific circumstances, after discussion with the Principal Investigator, one of the two medications can be discontinued for safety. Documentation of the reason(s) study drug is discontinued is required. Other dose modifications may be considered as clinically indicated with documentation and approval of the PI.

Hematologic toxicity:

Ruxolitinib may be administered and dose adjusted as per standard practice (see Tables below). Reductions in dosing for therapy related anemia can be done at the discretion of the investigator

Ruxolitinib dose modifications recommended for patients with starting platelet count of at least $100 \times 10^9/L^*$

	Dose at time of decline in platelet count					Maximum dose based on platelet count after prior treatment interruption or dose reduction
	25 mg BID	20 mg BID	15 mg BID	10 mg BID	5 mg BID	
Current platelet count	New dose to be used					

$\geq 125 \times 10^9/L$	No change	20 mg BID				
100 to $<125 \times 10^9/L$	20 mg BID	15 mg BID	No change	No change	No change	15 mg BID
75 to $<100 \times 10^9/L$	10 mg BID	10 mg BID	10 mg BID	No change	No change	10 mg BID for 2 weeks; if stable, may increase to 15 mg BID
50 to $<75 \times 10^9/L$	5 mg BID	5 mg BID	5 mg BID	5 mg BID	No change	5 mg BID for 2 weeks; if stable, may increase to 10 mg BID
$<50 \times 10^9/L$	Hold	Hold	Hold	Hold	Hold	Continue holding

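### Section 5.0 keeps patients on the previous ruxolitinib dose until new supply arrives and exempts only holds; read literally, it also defers the platelet-driven reductions of Section 5.1

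*Combined protocol and SAP*

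**What the plan says.** The supply sentence stands at the end of the first paragraph of Section 5.0 (Treatment Plan). It opens "When a dosage change of the Ruxolitinib is indicated (except for holding therapy due to toxicity") and continues that "patients will continue taking their previously prescribed dosing level until the new supply of Ruxolitinib is available for use by the patient". It makes no distinction between increases and decreases.

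Later in Section 5.0 the reader is sent elsewhere for dose changes: "Guidelines for reducing or increasing dosages are described in Section 5.1". Section 5.1 (Dose Modification) then gives two ruxolitinib tables, both described as recommended. The first, for starting platelets of at least 100 × 10⁹/L, lists under "New dose to be used" a lower dose in three platelet bands between 50 and <125, and a hold only below 50. The second covers starting platelets from 50 to below 100; for these patients Section 5.0 says "gradual up-titration from a starting dose of 5 mg BID is recommended".

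Section 5.1 also allows discretionary reductions: "Reductions in dosing for therapy related anemia can be done at the discretion of the investigator", and "The dose of therapeutic agents can be decreased at the discretion of treating physician, for chronic grade 2 non-hematologic toxicity".

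**The concern.** The sentence carves out one toxicity action, the hold, and leaves the other, the reduction, under the rule that the old dose continues. If staff follow the text, a patient whose platelets have fallen into a reduction band stays on the higher dose for as long as resupply takes.

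Falling counts are to be expected here. Section 2.1 notes that ruxolitinib can cause anemia or thrombocytopenia in a significant share of patients. Section 3.2 links pracinostat, added from cycle 4, to thrombocytopenia, and Section 2.3 reports grade 3-4 thrombocytopenia in 21% of the earlier pracinostat study in myelofibrosis. Section 3.1 says ruxolitinib comes through commercial supply after insurance approval, so some wait is plausible. What is at stake is patient safety on the background drug.

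**Working it through.** No figure in the plan needs reproducing. The check has two parts.

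**1. Does any other text take reductions out of the rule?**

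- Section 5.0 refers reductions to Section 5.1 but does not say which section prevails. The supply sentence is worded as what patients will do; the Section 5.1 ruxolitinib tables are recommendations.
- Section 5.2 allows ruxolitinib at 5 mg QD or 5 mg BID, but for patients waiting to start a new pracinostat cycle, not for patients waiting for ruxolitinib tablets.
- Section 5.6 requires dose adjustments to follow the protocol unless discussed with the principal investigator. That leads back to the same sentence. Its rules for outside physicians require dose changes to be approved by the center's physician, but say nothing about supply.
- No section limits the wait.

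**2. Which doses are affected, and by how much?**

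Input: the first Section 5.1 table, with five current doses and five platelet bands. Ratio = daily dose continued ÷ daily dose recommended, in mg/day (twice the BID dose). The top row, which appears as one merged entry, is read as no change in all five columns.

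| Platelets (× 10⁹/L) | 25 mg BID | 20 mg BID | 15 mg BID | 10 mg BID | 5 mg BID |
|---|---|---|---|---|---|
| ≥125 | no change | no change | no change | no change | no change |
| 100 to <125 | 50/40 = 1.25 | 40/30 = 1.33 | no change | no change | no change |
| 75 to <100 | 50/20 = 2.5 | 40/20 = 2 | 30/20 = 1.5 | no change | no change |
| 50 to <75 | 50/10 = 5 | 40/10 = 4 | 30/10 = 3 | 20/10 = 2 | no change |
| <50 | hold | hold | hold | hold | hold |

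- Reductions: 2 + 3 + 4 = 9. Holds (exempt): 5. No change: 5 + 3 + 2 + 1 = 11. Total 25.
- In the 15 and 20 mg BID columns, which are the protocol's starting doses: reductions 1 + 2 + 2 = 5, holds 2, no change 3; total 10.

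The length of the wait is not in the documents. As an illustration only, assume 0 to 14 days at platelets 50 to <75. From 15 mg BID the excess is 30 − 10 = 20 mg/day, so 0 to 280 mg in total. From 20 mg BID it is 40 − 10 = 30 mg/day, so 0 to 420 mg. It is zero if tablets on hand can make up the lower dose and the patient starts it at once.

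The next scheduled blood count is 2 weeks away in cycles 1-6 and one cycle (4 weeks) away afterwards, unless an extra one is ordered (Section 5.6).

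**The case against.** The strongest reply is that this is a logistics sentence and should be read with its surroundings. The same paragraph lets the treating physician raise or lower ruxolitinib before pracinostat starts and points to Section 5.1. That section adjusts ruxolitinib by standard practice, with a table keyed to the current platelet count. On that reading Section 5.1 sets the dose, and the supply sentence covers only a change the patient cannot yet make. This is probably what was intended. But the sentence does not say so, and even on this reading a patient without suitable tablets is told to keep taking the higher dose.

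It is also true that no protective option is removed. A hold for toxicity is exempt at any count, and another modification can be made with the principal investigator's approval. That stands and limits the severity. It leaves the less safe action as the written default.

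Two further points stand. Anemia and chronic grade 2 reductions are optional, so deferring them breaches no required step. Patients in the low-platelet stratum are mostly dosed in 5 mg units and could probably reduce without new tablets; no size is claimed for the second table.

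A reader might infer that over a third of patients would be overdosed (9 of 25), or that three- to fourfold over-exposure is to be expected. The documents do not support either. Cells are not patients, and the 3- and 4-fold cases need platelets to reach 50 to <75 before any intermediate reduction has taken effect. Nor does Section 3.1 say that each dose change needs fresh insurance approval.

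**Conclusion.** The point holds as a minor patient-safety wording error. Followed literally, Section 5.0 defers the reductions in 9 of the 25 cells of the first Section 5.1 table, 5 of them from the 15 or 20 mg BID starting doses, without a time limit.

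The conclusion about the wording rests on the text alone. Any actual over-exposure rests on two facts the documents do not give: whether tablets on hand can make up the lower dose, and how long resupply takes. Its frequency, duration and size are therefore unknown.

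A reader might also infer that the sentence weakens the main safety rules or the trial's statistics. It does not. Holds, the mandatory interruption for drug-related grade 3-4 non-hematologic toxicity, and the stop of both drugs at platelets ≤25 or ANC ≤0.5 × 10⁹/L on the combination are unaffected. The primary endpoint, the sample size and the stopping boundaries do not depend on the sentence.

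**What to change.** Change the exception in Section 5.0 to: *except for holding therapy or reducing the dose due to toxicity or blood counts*. Then add: *A reduced dose starts at once from existing tablets where strengths allow; where they do not, the treating physician decides between a temporary hold and the nearest achievable lower dose until new supply arrives.* The supply sentence then governs only increases and other changes not made for safety.

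No platelet threshold for an automatic hold should be added. The Section 5.1 tables recommend a reduced dose, not a hold, at 50 to <75 (first table) and generally at 25 to <35 (second table), and the documents give no basis for overriding them.

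This is a cheap improvement: two sentences, with no extra patients, visits or data fields, since site staff already "record the number of capsules/tablets and strengths returned". The downside is an occasional short hold of ruxolitinib, at the physician's discretion, while tablets are awaited.

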5.1 Dose Modification

Non-hematologic toxicity:

If drug-related grade 3 or 4 non-hematologic toxicity is attributable to one or both of the drugs, dose interruption of the drug(s) causing the toxicity, as assessed by the treating physician, is mandatory. Patient who experience grade 3 drug related non-hematological toxicity may be given a subsequent course one dose level below the previous course, but the patient must have recovered to grade </=1 or baseline before institution of the next course. If a patient has drug-related grade 4 non-hematologic toxicity, he/she may receive a subsequent courses at one reduced dose level after resolution of toxicity to grade </=1, only if approved by the Principal Investigator based on the clinical significance of the toxicity and only if patient has had derived a benefit from the therapy. The dose of therapeutic agents can be decreased at the discretion of treating physician, for chronic grade 2 non-hematologic toxicity. In specific circumstances, after discussion with the Principal Investigator, one of the two medications can be discontinued for safety. Documentation of the reason(s) study drug is discontinued is required. Other dose modifications may be considered as clinically indicated with documentation and approval of the PI.

Hematologic toxicity:

Ruxolitinib may be administered and dose adjusted as per standard practice (see Tables below). Reductions in dosing for therapy related anemia can be done at the discretion of the investigator

Ruxolitinib dose modifications recommended for patients with starting platelet count of at least $100 \times 10^9/L^*$

	Dose at time of decline in platelet count					Maximum dose based on platelet count after prior treatment interruption or dose reduction
	25 mg BID	20 mg BID	15 mg BID	10 mg BID	5 mg BID	
Current platelet count	New dose to be used					

$\geq 125 \times 10^9/L$	No change	20 mg BID				
100 to $<125 \times 10^9/L$	20 mg BID	15 mg BID	No change	No change	No change	15 mg BID
75 to $<100 \times 10^9/L$	10 mg BID	10 mg BID	10 mg BID	No change	No change	10 mg BID for 2 weeks; if stable, may increase to 15 mg BID
50 to $<75 \times 10^9/L$	5 mg BID	5 mg BID	5 mg BID	5 mg BID	No change	5 mg BID for 2 weeks; if stable, may increase to 10 mg BID
$<50 \times 10^9/L$	Hold	Hold	Hold	Hold	Hold	Continue holding

* Starting ruxolitinib doses of 15 mg BID for patients with platelet counts of 100 to $200 \times 10^9/L$ and 20 mg BID for those with a platelet count $>200 \times 10^9/L$. Recommended dose modifications based on US prescribing information.

For insufficient response, doses may be increased in 5-mg BID increments to a maximum of 25 mg BID, provided that platelet and neutrophil counts are adequate. BID: Twice daily

Ruxolitinib dose modifications recommended for patients with a starting platelet count of at least $50 \times 10^9/L$ but less than $100 \times 10^9/L$ *

Current platelet count	Dosing recommendation
$<25 \times 10^9/L$	Interrupt treatment
25 to $<35 \times 10^9/L$ AND $<20\%$ decrease during the prior 4 weeks	Decrease dose by 5 mg QD or maintain the current dose if it is 5 mg QD
25 to $<35 \times 10^9/L$ AND $\geq 20\%$ decrease during prior 4 weeks	Decrease dose by 5 mg BID or use 5 mg QD if the current dose is 5 mg BID or QD
$\geq 40 \times 10^9/L$ AND $\leq 20\%$ decrease during prior 4 weeks, ANC $>1 \times 10^9/L$, AND no dose reductions or treatment interruptions for AE or hematologic toxicity during the prior 4 weeks	Increase dose by increments of 5 mg QD to a maximum of 10 mg BID if response is insufficient

* Starting ruxolitinib dose of 5 mg BID. Recommended dose modifications based on US prescribing information.

See full prescribing information for a complete description of US Food and Drug Administration FDA-approved dosing of ruxolitinib in patients with intermediate or high-risk MF.

AE: Adverse event; ANC: Absolute neutrophil count; BID: Twice daily; QD: Once daily.

While a patient is on both medications concurrently, dosing of-pracinostat as well as ruxolitinib will be discontinued for platelet counts $\leq 25 \times 10^9/L$ OR for ANC $\leq 0.5 \times 10^9/L$. Patients who experience platelet count $\leq 25 \times 10^9/L$ or ANC $\leq 0.5 \times 10^9/L$

Dose Level	Pracinostat
Level 0	60 mg
Dose Level -1	45 mg

during a cycle of therapy, will have a dose reduction of pracinostat by one dose level for subsequent cycles (see Table below).

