5.2 Initiation of a new cycle of pracinostat and ruxolitinib

A new course of pracinostat may begin on the scheduled Day 1 of a new cycle if:

- The ANC is $\geq 0.5 \times 10^9/L$
- The platelet count is $> 25 \times 10^9/L$,
- Any drug-related grade 3-4 adverse event that may have occurred has resolved to \leq grade 1 severity or baseline
- Normal potassium and magnesium serum levels (hypokalemia or hypomagnesemia should be corrected prior to pracinostat administration)
- QTcF interval < 500 msec (reversible causes of QTc prolongation should be corrected, e.g. hypomagnesemia and hypokalemia, and ECG repeated. Provided that the patient is asymptomatic and that QTc decreases below 500 msec, pracinostat administration may continue).

If these conditions are not met on Day 1 of a new cycle, the subject will continue ruxolitinib alone (see guidelines for restarting/continuing ruxolitinib in the next paragraph) and be evaluated weekly and a new cycle of pracinostat will not be initiated until the toxicity has resolved as described above. If pracinostat dosing was interrupted during the previous cycle or if the new cycle is delayed due to toxicity newly encountered on the scheduled Day 1, then the new cycle of pracinostat will be started when the criteria above are met AND with at least a one-level dose reduction.

Treatment with ruxolitinib may restart/continue at 5mg QD so long as $ANC > 0.5 \times 10^9/L$ AND platelets $> 25 \times 10^9/L$ (with approval of Principal Investigator, and documented) or at 5mg BID so long as $ANC \geq 1 \times 10^9/L$ AND platelets $> 50 \times 10^9/L$ while waiting to initiate a new cycle of pracinostat. If the toxicity has not resolved as described above within 8 weeks of the scheduled start date for the new cycle of pracinostat, the patient may discontinue treatment with pracinostat and continue therapy with ruxolitinib alone. In unusual circumstances this rule may be modified by the Principal Investigator if felt to be in the best interest of the patient (for example, responding patient with neutropenia or low platelets, that resolve past 8 weeks may be restarted on therapy); such case must be fully documented.

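### At an ANC of exactly 0.5 × 10⁹/L, Section 5.2's ANC criterion permits a new pracinostat course although Section 5.1 stops both drugs at that count

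*Combined protocol and SAP*

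**What the plan says.** Two sections govern pracinostat at low counts.

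- **Section 5.1, hematologic toxicity (stop rule).** "While a patient is on both medications concurrently, dosing of-pracinostat as well as ruxolitinib will be discontinued for platelet counts" of 25 × 10⁹/L or less, or for an ANC of 0.5 × 10⁹/L or less. A patient who reaches either limit "during a cycle of therapy, will have a dose reduction of pracinostat by one dose level for subsequent cycles". The only step in the table is from 60 mg to 45 mg.
- **Section 5.2 (start rule).** "A new course of pracinostat may begin on the scheduled Day 1 of a new cycle if" five conditions hold. The ANC condition reads "The ANC is $\geq 0.5 \times 10^9/L". The platelet condition is a count above 25. The third condition is that any drug-related grade 3-4 adverse event has come down to grade 1 or less, or to baseline. The other two concern electrolytes and QTcF.

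If the Section 5.2 conditions are not met on Day 1, the patient stays on ruxolitinib alone, subject to that section's ruxolitinib limits, and is to "be evaluated weekly and a new cycle of pracinostat will not be initiated until the toxicity has resolved as described above". If pracinostat was interrupted in the previous cycle, or "if the new cycle is delayed due to toxicity newly encountered on the scheduled Day 1", the next course starts at least one dose level lower.

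For ruxolitinib during that wait, Section 5.2 says "Treatment with ruxolitinib may restart/continue at 5mg QD so long as" the ANC is above 0.5 and platelets are above 25, with documented Principal Investigator approval.

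**The concern.** The stop rule and the start rule for the same drug should divide the range of counts between them, so that no count falls under both. For platelets they do. For ANC both limits include 0.5, so a patient whose ANC is exactly 0.5 on Day 1 passes the ANC line of the start list while already meeting the rule that stops both drugs.

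The start list is the natural reference on Day 1. Weekly evaluation and the reduction after a Day 1 delay follow only when one of its conditions fails, and at 0.5 the ANC line does not fail. If the course is started, the Section 5.1 reduction applies to subsequent cycles and not to the course being started. What is at stake is therefore whether a patient at the stop threshold begins a course or waits and restarts lower.

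**Working it through.** The plan gives no figure to reproduce. The check compares the inequalities as written (counts in × 10⁹/L).

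**Inputs**

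- Stop both drugs: ANC ≤ 0.5, or platelets ≤ 25 (Section 5.1).
- Start pracinostat: ANC ≥ 0.5 and platelets > 25, plus the other conditions (Section 5.2).
- Ruxolitinib 5 mg once daily while waiting: ANC > 0.5 and platelets > 25 (Section 5.2).

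**ANC, with platelets above 25**

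| ANC | 5.1 stop rule | 5.2 pracinostat ANC criterion | 5.2 ruxolitinib 5 mg once daily, ANC part | Pracinostat stop and start |
|---|---|---|---|---|
| 0.49 | met | not met | not met | agree |
| 0.50 | met | met | not met | overlap |
| 0.51 | not met | met | met | agree |

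The counts at which both pracinostat rules hold are {ANC ≤ 0.5} ∩ {ANC ≥ 0.5} = {0.5}, a single value.

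**Platelets, with ANC above 0.5**

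| Platelets | 5.1 stop rule | 5.2 pracinostat platelet criterion | Pracinostat stop and start |
|---|---|---|---|
| 24 | met | not met | agree |
| 25 | met | not met | agree |
| 26 | not met | met | agree |

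Here {≤ 25} ∩ {> 25} is empty.

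**Which sign is out of line.** At ANC 0.50 the ruxolitinib rule refuses even 5 mg once daily, while the pracinostat ANC line is satisfied. Section 5.1, the platelet pair and the ruxolitinib rule all treat the threshold value as too low to dose. Only the pracinostat ANC start criterion treats it as acceptable.

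**Does the word concurrently in Section 5.1 remove the overlap?** No. A patient who starts a pracinostat course while taking ruxolitinib is on both drugs from that moment, so the stop rule applies at once on the same count.

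**After the correction.** With the start criterion at ANC > 0.5, {ANC ≤ 0.5} ∩ {ANC > 0.5} is empty, and all three comparisons agree at every value.

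**The case against.** The strongest reply is that the sections do not give conflicting orders. Section 5.1 is mandatory and Section 5.2 is permissive, so a reader who knows both withholds pracinostat and complies with both. That stands. A reader might infer that staff are given an impossible instruction, but the text supports only a permission that is one value too wide.

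The third start condition may also close the gap. It is not limited to non-hematologic events, and Section 5.2 later mentions neutropenia and low platelets among problems that may resolve late. Entry required an ANC of at least 1 × 10⁹/L (Section 4.0), so 0.5 is not an enrollment baseline. If the site grades the neutropenia 3-4 and calls it drug-related, the course is already blocked, weekly evaluation follows, and so does the lower restart dose if the toxicity is newly found on Day 1 or dosing was interrupted in the previous cycle. This stands in part. The protocol names CTCAE version 4.0 but does not print its limits, and attribution is left to the investigator. Neutropenia attributed to the disease would not be caught. So it cannot be said that weekly evaluation is never triggered at 0.5, only that the ANC line does not trigger it.

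A reader might also infer that such a patient would be dosed for weeks, until the next scheduled blood count. The documents do not support that. It requires that nobody applies the Section 5.1 stop to a count already in hand and that no extra count is taken.

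Finally, the protocol accepts a start at 0.51, and nothing in it shows a clinical difference between 0.50 and 0.51. That limits the weight of the point but does not reconcile the two rules.

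**Conclusion.** The overlap is real and confined to one value, ANC 0.5 × 10⁹/L. It is a minor dosing-safety correction, worth making because the threshold is operative and the other limits in the two sections show which sign is out of line.

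The documents do not allow an estimate of how many patients would have this value on Day 1. If the laboratory reports to one decimal (an assumption), a reported 0.5 stands for true counts of about 0.45 to 0.55, so the value is not merely theoretical.

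The conclusion assumes that the other start conditions are met, including that the neutropenia is not already blocking the course as a drug-related grade 3-4 event. Because it turns on one sign, confirm that the approved protocol prints the criterion as at or above.

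A reader might infer from a faulty safety threshold that the trial's monitoring is affected. It is not. The toxicity rule in Section 8.0 is defined on clinically relevant grade 3-4 non-hematologic toxicity or related serious adverse events, and no ANC dosing limit enters the sample size of 25 or the boundaries in Table 1.

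**What to change.** In Section 5.2, change the pracinostat start criterion to ANC > 0.5 × 10⁹/L. Leave the minimum ANC of 0.5 for clinical improvement in the Section 6.0 footnotes as it is; that is a response criterion, not a dosing rule.

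Lowering the Section 5.1 stop to ANC < 0.5 would also remove the overlap, but it needs two edits there, leaves the ruxolitinib rule out of step, and moves in the less cautious direction.

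The cost is one inequality sign and its clinical consequence. A patient with an ANC of 0.5 on Day 1 is delayed, evaluated weekly, and restarted at least one level lower (60 mg to 45 mg). For a patient already at 45 mg the table has no lower level, but that limit already exists for any patient who meets the Section 5.1 stop rule at 45 mg. Sample size, stopping boundaries and analyses are unchanged.
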